4.1.2. Dose Expansion Phase

The expansion phase will evaluate the antitumor activity of surufatinib, and evaluate the safety and tolerability of surufatinib at the RP2D determined at the end of the dose escalation phase.

Approximately 115 additional patients will be enrolled into the 4 open-label treatment arms during this phase: at least 30 patients with advanced BTC that have progressed on standard first-line chemotherapy will be assigned to Arm A, at least 15 patients with advanced pNET that have progressed on either everolimus, sunitinib, or both will be assigned to Arm B, and at least 15 patients with advanced epNETs that have progressed on everolimus will be

CCI

assigned to Arm C, and at least 55 patients with STS will be assigned to Arm D.

The safety of all enrolled patients will be closely monitored from the time of the initial dose of investigational treatment until 30 days after the last treatment dose. Any SAEs that occur after the ICF is signed, but before the first dose of study drug is taken, should also be reported. All AEs will be graded in accordance with the NCI CTCAE v. 4.03.

Patients will receive surufatinib continuously by 28-day treatment cycles until disease progression (according to RECIST Version 1.1), death, intolerable toxicity, or at investigator's discretion that the patient can no longer benefit from the study treatment. Tumor assessments will be conducted according to RECIST v. 1.1 criteria at screening, Cycle 2 Day 1 and every 8 (± 1) weeks thereafter. Confirmation of CR and PR is required at no less than 4-week intervals between the date of initial response/progression and the confirmation assessment date.

4.2. SAMPLE SIZE

The total number of patients enrolled will depend on the number of dose escalations and the need to further characterize individual cohorts in the expansion phase.

Approximately 95-150 patients will be enrolled in this two-phase study: 35 patients in the dose escalation phase and approximately 115 additional patients in the dose expansion phase. The actual enrollment number may vary, depending on the number of dose levels evaluated and the number of DLTs observed in each cohort, as well as the potential need to further characterize individual cohorts in the dose expansion phase.

As per Protocol Amendment 7, an additional 15 patients will be enrolled into Arm A (BTC) of the expansion phase, for a total enrollment of at least 30 advanced BTC patients. The reason for increasing enrollment into Arm A (advanced BTC) is that preliminary data from the ongoing patients in this cohort have shown encouraging results. The additional patients will allow further characterization of the safety and efficacy of surufatinib in this patient population. Arm B (pNET) and Arm C (epNET) will enroll at least 15 patients each. If needed, Arm B and Arm C could enroll additional patients in order to characterize further the safety and efficacy of surufatinib in these patient populations.

As per Protocol Amendment 8, 45 patients with STS (10 patients with Leiomyosarcoma (LMS), 10 patients with Undifferentiated pleomorphic sarcoma (UPS), 10 patients with epithelioid sarcoma, 10 patients with angiosarcoma, 10 patients with synovial sarcoma, and 5 patients with Pigmented villonodular synovitis (PVNS)) are planned to be

CCI

enrolled.

As per Protocol Amendment 10, an additional 10 patients will be added to the arm D (STS) for a total enrolment of 55 patients.

Additional details on sample size can be found in Protocol Section 10.1.

4.3. SCHEDULE OF EVENTS

Schedule of events can be found in Protocol Appendix 1 - Study Flowcharts.

4.4. CHANGES TO ANALYSIS FROM PROTOCOL

Additional Analysis for ECG will be included the evaluation of change from baseline in QTcF (Δ QTcF) intervals and the relationship between QT/QTc and RR intervals at baseline will be evaluated graphically. Refer to the section 17.3.3 and 17.3.4 for the details.

5. PLANNED ANALYSES

The following formal analyses are planned for the study:

[figure not shown]
5.1. SAFETY REVIEW COMMITTEE (SRC)

Safety monitoring and evaluation for dose escalation will be carried out by a Safety Review Committee (SRC) upon completion of the DLT observation period of each cohort.

The SRC is chaired by the Sponsor's Clinical Program Leader of the surufatinib program, and members will include the principal investigators (PIs), the Sponsor's PK scientist, medical monitor, and safety scientist, and the CRO's medical monitor. Dose escalation decisions are based on safety and PK data from this ongoing trial, as well as consideration of safety and PK data at comparable drug exposures from patients in previously conducted clinical trials in China.

For the dose expansion phase of the trial, a separate, specific SRC will be established to ensure the safety of all patients treated with study drug in the STS cohort (STS-SCR). Review of available safety laboratories, adverse events, and any other pertinent data available will be reviewed after the first 4 patients in each sarcoma cohort have completed at least 1 cycle of treatment. The recommendations of the STS-SRC will be based on the members'

CCI

clinical assessment of the cumulative safety data provided for review. The SRC will not be charged with the application of formal statistical stopping rules for safety.

5.2. INTERIM ANALYSIS

An informal interim analysis was performed using data cut-off date of 30JUN2020. This SAP covers the analyses for efficacy and safety based on the data cut-off for the interim analysis. The interim analysis was performed using cleaned eCRF data collected until data cut-off date. In addition, SAEs were be summarized based on all patients recruited into study on or before data cut-off date. All SAE data to be included in the interim analysis was to be cleaned.

Considering the goal of this interim analysis was to support regulatory submission, the efficacy analysis for this interim analysis was limited to pNET and epNET cohorts while the safety was cover all patients enrolled on the trial as of the planned cut-off date.

In addition, the overall survival analysis for BTC and STS cohorts were not included in this interim analysis. The tumor assessment after the end of treatment was not applied to this interim analysis as well. The tumor assessment data after the end of treatment was cut-off for this interim analysis.

5.3. SNAP SHOT ANALYSIS

A snap shot analysis was performed using data at cut-off date of 14Jun2019.

All summaries of safety and efficacy data were presented by assigned dose level in escalation phase, and disease type which pooled the patients who enrolled in the dose expansion phase and patients of the same tumor type (BTC, pNET, epNET) at the RP2D dose level in the dose escalation phase.

5.4. FINAL ANALYSIS

All final, planned analyses identified in this SAP will be performed by IQVIA Biostatistics by following sponsor's authorization of this SAP and final Database Lock (DBL) for this study.

6. ANALYSIS SETS AND PROTOCOL DEVIATIONS

Agreement and authorization of patients included/ excluded from each analysis set will be conducted prior to the

CCI

DBL for the final analysis of the study.

All summaries will be presented by assigned dose level in escalation phase, and by disease type which will pool the patients who enrolled in the dose expansion phase and patients of the same tumor type (BTC, pNET, epNET, STS) at the RP2D dose level in the dose escalation phase.

All patients will be presented according to their initial assigned dose level regardless of any dose adjustment during study conduct.

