Appendix A	Study Flowchart	Added column for C1D16, pre-dose PK sample, and provided a copy of the PK sampling schedule sampling times. Added copy of Table 12 (PK Sampling Times) at the end of the study flowchart.
		Corrected spelling and/or grammatical errors in the document as needed.

Protocol Amendment 6 (Version 3.0, 30 May 2018):

Summary of Changes: Protocol Amendment 6 (Version 3.030 May 2018)
Specified initial dose of study drug in dose expansion phase as 300 mg QD. Per SRC review of data for patients treated with 300 mg QD, specified option of escalation to 400 mg QD for patients in dose expansion phase with decrease in tumor size but not enough to achieve CR or PR and no SAE or any AE \geq Grade 3 after 3 cycles on 300 mg QD.
Added 6 more patients in 400 mg cohort in the dose escalation phase
Specified the study population, the target number of patients to be enrolled in the dose escalation and expansion phases, and the number of sites needed to enroll the patients in a timely fashion
Specified planned enrollment of approximately 65-70 patients.
Specified the study population, the target number of patients to be enrolled in the dose escalation and expansion phases, and the number of sites needed to enroll the patients in a timely fashion
Updated the number of investigational sites.
Stipulated that the term “tumor assessment” would be used throughout the protocol; that tumors would be assessed according to RECIST V. 1.1 at Screening, Cycle 2 Day 1 (C2D1), and every 8 (± 1) weeks thereafter.
Specified dose adjustment for impaired liver function.
Specified tumor markers to be assessed: CEA and CA 19-9 for patients with BTC (Arm A) and chromogranin-A for patients with pNET (Arm B).
Changed PK sampling times on C1D1, C1D15 and C2D1 post-dose 12 hours (± 60 minutes) to post-dose 6 hours (± 60 minutes)
Added chemistry panel and urinalysis to study flowchart C1D8 and C1D22 for safety monitoring.
Added study visit windows: Day 8 (D8), D15, D22 of Cycle 1 and D1, D15 of Cycle2 (± 1 d); Cycle 3 and onwards: D1 (± 3 day) and then every 4 weeks.
Added the dose modification guideline to Section 5.2.2. Specified dose modification guideline for proteinuria and for Grade 3 liver function impairment.

Protocol Amendment 5 (Version 2.0, 8 December 2017): Summary of Changes: Protocol Amendment 5 (Version 2.0, 8 December 2017)
Specified study population, target number of patients to be enrolled in the dose expansion phase and the number of sites needed

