5.1.2 Dose Expansion Phase

The expansion phase will evaluate the anti-cancer activity of surufatinib, and confirm the safety and tolerability of surufatinib at the RP2D determined at the end of the dose escalation phase.

Under amendment 7 of this protocol, the MTD was declared when 2 of the 6 DLT evaluable patients in Cohort 7 (400 mg QD dose) of the dose escalation phase reported DLTs. There was an ad hoc meeting of the SRC on 30 November 2018. The SRC agreed with the declaration of 300 mg QD as the MTD of surufatinib in this trial and agreed that 300 mg QD is the RP2D going forward. The minutes of this ad hoc SRC meeting were distributed to all investigative sites on the same day. It was also agreed that patients who were already receiving 400 mg QD could remain on this dose, provided that 1) there was no major toxicity and 2) the affected patients gave informed consent not to reduce the dose to 300 mg after discussion with the investigator. However, no patients could have their dose escalated to 400 mg going forward, including all patients in the dose expansion phase.

The safety of all enrolled patients will be closely monitored from the time of the initial dose of investigational treatment until 30 days after the last treatment dose. Any SAEs that occur after the informed consent form (ICF) is signed, but before the first dose of study drug is taken, should also be reported. All AEs will be graded in accordance with the NCI CTCAE v. 4.03. Tumor assessments will be conducted according to RECIST Version 1.1 criteria at screening, Cycle 2 Day 1 and every 8 (± 1) weeks thereafter. Confirmation of

CR and PR is required at no less than 4-week intervals between the date of initial response/progression and the confirmation assessment date.

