10.2 Analysis Populations

The following analysis populations have been defined for the study:

- Note: the **DLT Evaluable Set** (dose escalation phase) is defined in [Section 5.1.1](#).
- **Safety Analysis Set (SAS) – (All Treated Population):** This population includes all patients who have received at least one dose of surufatinib. Safety data will be evaluated based on this population's outcome. Patients in the SAS will be analyzed by their actual dose initially received. If patients have dose reduction during the study, all data will be summarized/analyzed based on the initial dose of

study drug received. Efficacy endpoints PFS and OS (OS applies to BTC and STS cohorts only) will be analyzed based on this population.

- **Pharmacokinetic Analysis Set (PKAS):** This population will include all patients who received at least one dose of surufatinib and have at least one PK sample obtained and analyzed.
- **Efficacy Analysis Set (EAS):** This population includes all patients who have received at least 1 dose of surufatinib and have had at least 1 post- baseline tumor assessment. All efficacy endpoints will be analyzed will based on this analysis set, except for PFS and OS, which will be analyzed based on SAS.

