4.1.1. Dose Escalation Phase

In this phase, a 3+3 design will be used. Enrollment of 35-40 patients was planned. As of Protocol Amendment 7, a total of 35 evaluable patients have been enrolled in the dose escalation phase. The trial was to evaluate 5 surufatinib dose levels at 50, 100, 200, 300 and 400 mg on a QD dosing schedule.

CCI

The study conduct was to follow a 3+3 design, with the dose limiting toxicity (DLT) assessment window being Cycle 1, from Day 1 to Day 28. Detailed description of a 3+3 design can be found in protocol section 5.1.1.

In addition to the five dose levels, in the occasion where 2 or more DLTs were observed in the 6 evaluable patients at a given dose level, the dose escalation was to be halted. If this dose level is greater than or equal to 50% higher than the previous dose level, an intermediate dose level was to be evaluated for toxicity in the same manner as a 3+3 dose level. If the dose level was less than 50% higher than the previous dose level, additional patients were to be enrolled at the previous dose level, if necessary, to form a dose cohort of minimum 6 evaluable patients. The MTD is the highest dose reached with no more than 1 DLT among 6 evaluable patients.

Any patient who was considered non-evaluable for DLT as defined in protocol section 5.1.1 'Dose escalation phase' was to be replaced by an additional patient at that same dose level.

Safety monitoring and evaluation for dose escalation will be carried out by a Safety Review Committee (SRC) upon completion of the DLT observation period of each dose level.

Patients who have completed the DLT observation window (Cycle 1, day 1-28) and were deemed to be benefiting from surufatinib treatment could have been permitted, at the investigator's discretion, to continue with surufatinib treatment until disease progression, death, intolerable toxicity, pregnancy, or loss of benefit from the study drug. Intra-patient dose escalation to a higher dose that had been cleared was allowed if the sponsor and investigator both agreed.

[figure not shown]
The MTD/RP2D of surufatinib has been declared at 300 mg QD (Protocol Amendment 7).

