6.2. SAFETY ANALYSIS SET (SAS) – (ALL TREATED POPULATION)

This analysis set includes all patients who have received at least one dose of surufatinib. Safety data will be evaluated based on this analysis set outcome. Patients in the SAS will be analyzed by their actual dose initially received. If patients have dose reduction during the study, all data will be summarized/ analyzed based on the initial dose of study medication received.

All safety analyses except for DLT summaries will be based on the SAS. Efficacy endpoints PFS and OS (OS applies to BTC and STS cohorts only) will be analyzed based on this analysis set.

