17.1.3. TEAEs Leading to Study Medication Adjustment

TEAEs leading to study medication adjustment will be identified as those records with a response of “Drug interrupted” or “Dose reduced” or ‘Dose increased’ to the item “Action taken with the study drug” on the AE/SAE form of the CRF.

For TEAEs leading to study medication adjustment, summaries of incidence (frequencies and percentages) by SOC and PT will be prepared. Summaries for TEAEs leading to study medication adjustment by SOC and PT will be further broken down by maximum severity and strongest relationship to study medication.

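### Starting-dose attribution extends to dose increases, so later-cycle safety data can be tabulated under a lower dose and 300 mg groups may contain unflagged 400 mg exposure

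*SAP*

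**What the plan says.** SAP Section 6 sets the attribution rule for all summaries: "All patients will be presented according to their initial assigned dose level regardless of any dose adjustment during study conduct". SAP 6.2 puts it differently for the safety set. Patients are analysed by the dose they actually received first, and then: "If patients have dose reduction during the study, all data will be summarized/ analyzed based on the initial dose of study medication received". Protocol 10.2 has the same pair of statements. Neither mentions increases.

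The SAP treats an increase as a kind of adjustment: Section 17.1.3 lists "Dose increased" beside interruption and reduction. Increases were possible in the escalation phase. SAP 4.1.1 says: "Intra-patient dose escalation to a higher dose that had been cleared was allowed if the sponsor and investigator both agreed". Protocol 5.1.1 places this permission with patients who continue after the 28-day DLT window.

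For the move to 400 mg, Protocol 5.1.2 reports the committee meeting of 30 November 2018. From then "no patients could have their dose escalated to 400 mg going forward, including all patients in the dose expansion phase", while, subject to conditions, "patients who were already receiving 400 mg QD could remain on this dose". As history only, the Amendment 6 summary "specified option of escalation to 400 mg QD for patients in dose expansion phase with decrease in tumor size", after three cycles at 300 mg.

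SAP 6 also pools escalation-phase patients treated at the RP2D into the disease groups of the same tumor type. SAP 16.4 plans no efficacy sensitivity analysis.

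**The concern.** Analysing by starting dose is sensible for reductions, because lowering the dose is usually a consequence of the starting dose. An increase works the other way. An event that appears after a patient moves up is credited to a dose the patient is no longer taking. Low dose levels can then take on toxicity that arose at a higher dose, and the by-dose safety comparison becomes harder to read.

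In expansion, the primary objective is activity in patients treated at 300 mg QD. If a patient counted at 300 mg spent time at 400 mg, the PFS and safety results for that group describe a mixture, and the reader of those tables would not know.

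**Working it through.** **1. Does the rule reach increases?** SAP 6 covers any adjustment, and SAP 17.1.3 includes increases among adjustments. Yes. SAP 6.2 and Protocol 10.2 name only reductions after their general sentence. SAP 6 speaks of the assigned dose and SAP 6.2 of the dose actually received first, so the two are not worded alike.

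**2. Who could have had an increase to 400 mg?** Dates are from the protocol's amendment history and Section 5.1.2.

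| Date | Event |
|---|---|
| 30 May 2018 | Amendment 6: option of 300 to 400 mg in expansion |
| 30 November 2018 | No further increases to 400 mg |
| 25 January 2019 | Amendment 7: Arm C added; Arm A raised from 15 to 30 |
| 4 September 2019 | Amendment 8: Arm D added |

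The candidates are the escalation-phase 300 mg level, its patients where pooled into disease groups, and Arm A or B patients treated before 30 November 2018. The 15 patients added to Arm A by Amendment 7, and everyone enrolled in Arms C and D, came after the stop. Increases between lower doses concern the escalation phase only.

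**3. Which outputs are affected?** Those that run past Cycle 1 by dose level or disease group: TEAE tables (SAP 17.1.1), shifts to worst laboratory grade (17.2.3), later QTcF changes and the mean QTcF change over time plotted by dose group (17.3.3), and PFS (16.2). DLT tables are not affected, because DLTs are confined to Days 1 to 28 (Protocol 5.1.1.3).

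**4. How much can one patient weigh?** Protocol 5.1.1 gives 35 escalation patients, 9 at 300 mg and 13 at 400 mg, so 35 − 9 − 13 = 13 remain across 50, 100 and 200 mg. A level has 3 to 6 patients in the 3+3 scheme.
- One event: 1/6 = 17% to 1/3 = 33% of a level's rate. This is the maximum, reached only if the patient had no such event before the increase.
- Arm A: 1/30 = 3.3 points. Arm B: 1/15 = 6.7 points. These assume that the increase alone decided the patient's PFS status, and use simple proportions in place of Kaplan-Meier estimates.

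**5. Would the planned exposure tables show it?** SAP 15 reports the number, timing and reasons for increases and groups relative dose intensity (RDI) as below 80%, 80 to 120%, and above 120%. With a share f of time at 400 mg and a planned dose of 300 mg:

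RDI = [300(1 − f) + 400f]/300 = 1 + f/3, so RDI > 1.2 needs f > 0.6.

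| Increase after | Time point | Days at 400 mg | f | RDI |
|---|---|---|---|---|
| Day 84 (3 cycles) | 16 weeks (112 days) | 28 | 25% | 108% |
| Day 84 | 11 months (335 days) | 251 | 75% | 125% |
| Day 28 | 16 weeks | 84 | 75% | 125% |
| Day 28 | 11 months | 307 | 92% | 131% |

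These are illustrations assuming no interruptions. A patient can spend over half of treatment at 400 mg and still fall in the 80 to 120% band. In addition, SAP 15.1 writes the length of each dosing record as start minus stop plus one. For Days 1 to 28 that is 1 − 28 + 1 = −26 instead of 28, so the formula behind RDI needs its sign corrected.

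The TEAE table in SAP 17.1.3 does not help either. It selects events by the action taken in response to them, not events that arose after an increase.

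**The case against.** Analysis by starting dose is a common convention, the study has no formal hypothesis test, and SAP 15 already reports increases with timing and reasons and flags dose modifications in the administration listings. All of that stands. It is why the starting-dose tables should remain the main ones and why part of the information is already planned. It does not close the gap, because none of those outputs links an event or a PFS time to the dose at that moment.

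A reader might infer that SAP 6 widens the protocol's rule without declaring it in SAP 4.4. The documents do not clearly support this. Before naming reductions, Protocol 10.2 says generally that safety-set patients are analysed by the dose first received, which can be read to cover increases. This is an unaddressed case, not an undeclared change.

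It may also be tempting to repeat PFS without the patients who were increased. The option recorded for Amendment 6 required tumor shrinkage short of a response and no SAE or Grade 3 or higher AE after three cycles. Dropping such patients would remove people because they were doing well and bias PFS downwards.

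Supplementary tables have limits too. Data cut at the increase have shorter follow-up and can miss delayed toxicity.

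**Conclusion.** The point holds for descriptive later-cycle safety by dose level and for the labelling of the 300 mg groups. As written, the plan credits post-increase data to the lower starting dose, and no planned safety or PFS output shows where this happened.

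The actual size is unknown. The per-patient weights above are ceilings, and the number of patients with an increase is not given and could be zero.

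Three stronger readings should be set aside:
- That the basis for the MTD or RP2D is distorted. It rests on DLTs in Cycle 1, and the documents describe increases only for patients continuing after that window.
- That expansion patients were in fact moved to 400 mg. No passage says so. The permission to remain on 400 mg equally describes the 13 patients enrolled at that dose in escalation.
- That all four arms are exposed. Arms C and D can be affected only through pooled escalation-phase 300 mg patients.

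The change is still worth making because the dosing records are already collected and the cost is small.

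**What to change.** - **SAP 6 and 6.2:** keep the starting-dose tables as the main presentation, state that the rule covers increases, and use one definition of starting dose (assigned or actually received) in both places.
- **SAP 17:** add supplementary dose-level summaries of TEAEs, worst-grade laboratory shifts and QTcF that cut each patient's data at the first dose increase, with follow-up time shown beside them.
- **300 mg level and pooled disease groups:** report how many patients exceeded 300 mg, and flag them in the safety and PFS outputs.
- **If there are any such patients:** add one PFS sensitivity analysis beside the primary estimate, censoring at the increase rather than excluding the patient. State that increases were selected on good outcome, so this censoring is itself informative. Amend SAP 16.4 to allow it.
- **SAP 15.1:** correct the sign in the record-length term.

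The cost is SAP wording and a few extra tables, with shorter follow-up in the cut tables. No new data are needed. If nobody had an increase, one sentence saying so makes the supplementary tables unnecessary.
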